3.3.4. Primary Efficacy Analyses

3.3.4.1. Primary Estimand

The primary estimand uses a treatment policy strategy that considers the efficacy response in subjects regardless of use of rescue medication.

Population:

Subjects with moderately-to-severely active CD [as defined by a CDAI score of 220-450 and SES-CD score of ≥ 6 (≥ 4 if isolated ileal disease) with ulceration (corresponding to a score of 1) in at least 1 of the 5 ileocolonic segments on the Presence of Ulcers subscore of the SES-CD] who are corticosteroid-dependent or have demonstrated inadequate response or intolerance to conventional therapy (aminosalicylates, corticosteroids and immunomodulators such as azathioprine, 6-mercaptopurine, or methotrexate) or biologics (e.g., anti-TNF therapy, anti-IL-12/23, anti-integrin). A subset of subjects (up to approximately 10%) will have an SES-CD score between 3 and 5 points, inclusive.

Variable:

Change from baseline in CDAI score at Week 12. Subjects with any of the following intercurrent events (ICE) prior to Week 12 will have data analyzed as collected following ICE under Treatment Policy approach.

Intercurrent events:

The following are the intercurrent events considered for this study:

Treatment Failure ICE:

1. Prohibited medication for AE of worsening CD (Section 5.7)
2. Any gastrointestinal resection
3. Increase in dose of oral corticosteroids for CD above baseline dose

4. Initiation of oral corticosteroids or aminosalicylates for CD where they were not ongoing at baseline
5. Discontinued study intervention due to AE of worsening CD or lack of clinical benefit

Other ICE:

6. Discontinued study intervention due to COVID-19
7. Discontinued study intervention for reasons other than COVID-19, AE of worsening CD or lack of clinical benefit
8. No attempt to taper steroids from Week 8

Population-level summary:

The mean difference in change from baseline CDAI score at Week 12 between each TD-1473 group and placebo.

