8.9. Handling of Missing Data

For the primary analysis of score change endpoints (e.g., CDAI score change, SES-CD score change), missing values will not be imputed. Sensitivity analyses for the primary endpoint will be specified in the SAP, and will be performed if one or both TD-1473 doses are shown to reduce Week 12 CDAI more than placebo.

Subjects with missing data for binary efficacy endpoints will be counted as treatment failures. Alternative approaches may be specified in the SAP.

In addition, subjects who had nonmissing data for a binary efficacy endpoint meeting the criterion for success but met one of the following criteria prior to the visit will be counted as treatment failures:

- Received rescue medication, defined as any medication given to treat CD symptoms, other than antidiarrheal medication for control of chronic diarrhea, if started postbaseline or if the dose was increased postbaseline to a dose higher than at baseline (both induction and ATE; ATE baseline is Week 12)
- Experienced disease worsening, defined as an increase in CDAI score from baseline of ≥ 100 points at consecutive visits (ATE only; ATE baseline is Week 12)

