3.4.4. Secondary Efficacy Analyses

3.4.4.1. Estimands

The treatment policy strategy that was used for the primary estimand for the primary endpoint analysis will be used for change from baseline in SES-CD Score at Week 12.

The remaining secondary endpoints of response/remission will be analyzed through a composite strategy as follows:

- Population: Same as primary estimand
- Variable: Endpoints(Section 3.4.1) and Definition (3.4.3)
- Intercurrent Events: For this estimand, meeting the criteria of an ICE (1-5) is considered an unfavorable outcome and subjects who meet these criteria prior to Week 12 will be considered not to be in response/remission.

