3.4.4.3. Missing Data Handling

For change in SES-CD at Week 12, missing data will be assumed MCAR there will be no imputation of missing data.

For binary endpoints missing data will be imputed with non-responder imputation with the exception of data missing due to COVID-19, in these instances the data will be assumed missing completely at random and not analyzed.

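### For the binary secondary endpoints, SAP intercurrent events 1–5 are narrower than the protocol's rescue-failure rule, so a few rescued subjects could be scored responders

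*SAP*

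**What the plan says.** Protocol 8.9 (Handling of Missing Data) counts missing binary outcomes as failures. It then adds a separate rule for observed outcomes: a subject "meeting the criterion for success but met one of the following criteria prior to the visit will be counted as treatment failures". The criterion that applies in Induction is "Received rescue medication, defined as any medication given to treat CD symptoms, other than antidiarrheal medication for control of chronic diarrhea, if started postbaseline", or raised after baseline to a dose above baseline. It sets no limit by route.

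SAP 3.4.4.1 handles observed binary outcomes through the intercurrent-event list: "meeting the criteria of an ICE (1-5) is considered an unfavorable outcome" when it happens before Week 12. The list is in SAP 3.3.4.1:

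- ICE 1: "Prohibited medication for AE of worsening CD (Section 5.7". The SAP section it points to is blacked out.
- ICE 2: gastrointestinal resection.
- ICE 3: "Increase in dose of oral corticosteroids for CD above baseline dose".
- ICE 4: "Initiation of oral corticosteroids or aminosalicylates for CD where they were not ongoing at baseline".
- ICE 5: "Discontinued study intervention due to AE of worsening CD or lack of clinical benefit".

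SAP 3.4.4.3 adds a rule for missing values only: "For binary endpoints missing data will be imputed with non-responder imputation with the exception of data missing due to COVID-19".

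Three other places bear on the point.

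- SAP 3.2.5 defines rescue for a descriptive summary. It covers added oral corticosteroids, aminosalicylates or antibiotics, oral corticosteroid increases, and prohibited medications. These count whether given for Crohn's disease itself or for an adverse event of its worsening.
- Protocol 6.4.30 lets a subject who newly starts a corticosteroid by any route for Crohn's symptoms during Induction stay on study drug.
- Protocol 4.2, criterion 400, excludes rectal and intravenous corticosteroids in the 14 days before Day 1.

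**The concern.** The protocol's failure rule turns on why a drug was given and when it was started. The SAP's list also turns on the route (ICE 3 and 4), on a recorded adverse event (ICE 1) or on stopping study drug (ICE 5). A subject can meet the first and none of the others.

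Four of the five secondary endpoints are binary and use this list: CDAI clinical response, CDAI clinical remission, endoscopic response and SFAP clinical remission. A subject whose Week 12 result may owe something to a steroid enema or an intravenous course would be a failure under the protocol and a responder under the SAP. If such rescue were more common on placebo, which is an assumption, the SAP rule would raise the placebo rate and shrink the treatment difference.

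The endpoints carry nominal p-values only. They still matter: Protocol 3.5.2 says the induction analysis is to inform the design of further studies, and Protocol 8.2 ties the 60-point CDAI target to an expected gain in clinical response.

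**Working it through.** **Tracing the rules.** In each case the subject starts the drug for Crohn's symptoms before Week 12, has no resection, stays on study drug and meets a binary criterion at Week 12.

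| Case | ICE 1 | ICE 3 | ICE 4 | ICE 5 | SAP result | Protocol 8.9 |
|---|---|---|---|---|---|---|
| Non-oral corticosteroid, no adverse event of worsening Crohn's recorded | No: no such event | No: not oral | No: not oral | No | Responder | Failure |
| Another prohibited Crohn's drug (say, an immunomodulator), no such event recorded | No: no such event | No | No | No | Responder | Failure |
| Non-oral corticosteroid, such an event recorded | Yes if SAP 5.7 lists it; blacked out | No | No | No | Cannot be settled | Failure |

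ICE 2 does not arise in any case. SAP 3.4.4.3 does not help, because the outcome is observed. The first two rows do not depend on the redacted list: ICE 1 needs the adverse event whatever SAP 5.7 contains. SAP 3.2.5 shows that the SAP itself separates use for Crohn's disease from use for an adverse event of worsening. If SAP 5.7 lists the drug, the rescue table would count the first two subjects as rescued while the response tables count them as responders.

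A subject already on a stable oral corticosteroid who adds an enema or an intravenous course also falls in the first row: no oral dose has risen and no oral drug is new.

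**Is the change declared?** Protocol 8.1 says changes to the planned analyses will be described in the SAP. SAP 5.1, the section for them, has a heading and no text. The sentence in Protocol 8.9 that allows alternatives in the SAP follows the missing-data rule; the rescue rule comes after it as an addition and has no such allowance.

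**Size.** The documents give no rate for this kind of rescue, so there is no figure to reproduce. The 82% and 58% power figures in Protocol 8.2 concern the primary endpoint and do not depend on this list. With the planned 40 placebo and 60 subjects per active arm:

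- One reclassified placebo subject: 1/40 = 2.5 percentage points.
- One reclassified active subject: 1/60 = 1.7 points.
- Standard error of a crude rate difference, √[p(1−p)(1/40 + 1/60)]: 8.2 points at an assumed common rate p = 0.2 and 10.2 points at p = 0.5. One placebo subject is therefore 2.5/10.2 = 0.24 to 2.5/8.2 = 0.31 of a standard error.
- If 5% of an arm were reclassified (assumption: 2/40 or 3/60, each 5.0 points), the difference moves by 0 if placebo and active are hit equally and by 5 points if only placebo is.
- For an assumed 0 to 4 subjects per arm, applying the protocol rule changes active minus placebo by between −4/60 = −6.7 points and +4/40 = +10.0 points.

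**The case against.** The best defence is that the list is a partition. SAP 3.2.5 puts oral corticosteroids in their own lines and prohibited medications in another, and ICE 1, 3 and 4 follow the same split. Protocol 6.4.30 opens by naming oral corticosteroid as the only rescue that lets a subject continue, and criterion 400 lists rectal and intravenous steroids among the excluded medications. Non-oral steroids may therefore well sit on the ICE 1 list. This largely stands. It means the verifiable gap comes at least as much from ICE 1's adverse-event condition as from the word oral in ICE 4. It does not close the gap, because that condition remains.

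Second, the case should be rare. Protocol 6.4.3 requires conditions that worsen after consent to be recorded as adverse events, so what is left is mainly treatment of persistent symptoms. The subject must also stay on study drug, which rests on one sub-item of Protocol 6.4.30 that sits badly with the sentence above it, and must still meet a Week 12 criterion. This stands and keeps the point small. That sub-item also says only that such a subject may be deemed a failure, but the analysis rule in 8.9 is firm.

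Third, Protocol 8.1 asks for changes to be described in the SAP, not in section 5.1 in particular, and the SAP states its own rule openly. That is fair. What is missing is any statement that the rule departs from 8.9, and a reason.

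A reader might infer that the SAP lets all non-oral steroid rescue through. The documents do not support that: ICE 1 may catch any case with a recorded adverse event of worsening Crohn's, and the list that would settle it is blacked out. A reader might also take ICE 3 as a second defect. It is not one in practice: rectal and intravenous steroids are excluded before Day 1, so in an eligible subject their use in Induction is a new start, which belongs under ICE 4.

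**Conclusion.** The point holds, and it is minor. For the binary secondary endpoints the SAP's failure list is narrower than Protocol 8.9. A subject given a non-oral corticosteroid or another prohibited drug for Crohn's symptoms, with no recorded adverse event of worsening Crohn's and still on study drug, can be scored a responder where the protocol says failure. No visible SAP text declares this.

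The size per subject is 2.5 points on placebo or 1.7 points in an active arm. This assumes the planned arm sizes. SAP Table 5 limits the mITT set by randomization date and drops two sites, so real denominators may be smaller and each subject may count for more. How many subjects are affected, and in which arms, is unknown; the conditions suggest few. The documents do not support a statement that the treatment difference is biased in a known direction.

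The primary analysis is unaffected, because it uses post-event data as collected. Supplementary Estimand 1 uses the same list and would keep the observed change for such a subject. Protocol 8.9 governs binary endpoints only, so there is no conflict there, but the reworded list would carry over to it.

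**What to change.** In SAP 3.3.4.1:

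1. Reword ICE 1 so that a prohibited medication counts when given to treat Crohn's disease or for an adverse event of its worsening, matching the purpose wording in SAP 3.2.5. This closes the gap for every drug listed in SAP 5.7.
2. Reword ICE 4 so that it covers new corticosteroids by any route, as well as new aminosalicylates, for Crohn's disease. State that a corticosteroid started by a new route is an initiation even if an oral one was ongoing. Non-oral steroids then count whatever SAP 5.7 lists, and steroids for other conditions stay out.
3. Leave ICE 3 as it is.
4. Two differences from Protocol 8.9 would remain: new antibiotics for Crohn's disease and aminosalicylate dose increases. Either add them to the list or declare them in SAP 5.1 with a reason.

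The cost is two reworded lines and one added clause, plus either a further list item or a short entry in 5.1. A few more subjects may be counted as failures on the binary endpoints and set to zero change in Supplementary Estimand 1. No data, visits or subjects are added, and the protocol's analysis rule need not change.

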3.3.4.2. Analysis Methods

The primary endpoint of CDAI score change from baseline at Week 12 will be analyzed based on the Primary Estimand by fitting a mixed effects repeated measures model using the change from baseline values at Weeks 4, 8, and 12 as the dependent variable. The model will include baseline CDAI score as a covariate and independent fixed effects for treatment group and prior biologics failure status (yes, no). The time effect of visit, the interaction of baseline CDAI score with visit and treatment with visit will also be included. Within-subject correlation will be modelled using an unstructured covariance structure. The Kenward and Roger method for approximating the denominator degrees of freedom will be used.

Summaries will be on the mITT population and include observed values, change from baseline values and least square (LS) means estimates. For testing of the primary endpoint, each TD-1473 dose versus placebo will be compared by displaying the LS mean difference estimate to placebo and associated 95% confidence interval. Nominal p-values will also be reported.

A CDAI score figure will also be presented with the LS mean change from baseline in CDAI score over time to Week 12 displayed. A placebo-adjusted figure will also be provided displaying the LS mean difference to placebo in CDAI score over time to Week 12.

A 2-group forest plot will summarize the LS mean difference from placebo in CDAI at Week 12 with 95% confidence interval. The forest plot will also display the differences from placebo for Supplementary Estimand 1 (Section 3.3.6.1) and Supplementary Estimand 2 (Section 3.3.6.2).

Graphical inspection of the model assumptions on the primary analysis will be performed and will include inspection of linearity of regression, equal variances and the independence and normality of errors. In the event that the assumptions are not met then p-values will be generated from the nonparametric randomization-based analysis of covariance methodology of [Koch et al. \(1998\)](#).

3.3.4.3. Missing Data Handling

Missing data (including data missing due to COVID-19) will be assumed missing at random (MAR) and accounted for through correlation of repeated measures.

3.3.5. Sensitivity Analyses

3.3.5.1. Sensitivity Analyses 1

To assess the impact of the MAR assumption on missing data a sensitivity analysis be performed assuming data is missing completely at random (MCAR) and not imputed. An analysis of covariance (ANCOVA) on change from baseline in CDAI score at Week 12 will be performed fitting an equal-slopes model with terms for prior biologics failure status, baseline CDAI score, and treatment.

3.3.5.2. Sensitivity Analyses 2

To assess the sensitivity of the treatment effect to the stool frequency component of the CDAI score, the primary analysis will be repeated where the CDAI score is calculated without the stool frequency component.

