8.5.2. Primary Efficacy Evaluations

The primary analysis of CDAI score change at Week 12 will be performed by fitting a mixed effects repeated measures model to values at Weeks 4, 8, and 12, with baseline CDAI score as a covariate, using SAS procedure MIXED to fit a model with random subject effects, an unstructured covariance matrix, and including terms for prior biologics failure status, visit, and baseline CDAI score by visit and treatment by visit interactions.

The effect of each TD-1473 dose on reduction in CDAI at Week 12 (and also at Week 4 and at Week 8) will be estimated. These estimates are unbiased if missing data are missing at random (MAR). This assumption will be assessed with a missing data sensitivity analysis if at least one TD-1473 dose is shown to reduce Week 12 CDAI more than placebo.

As a sensitivity analysis, CDAI score change at Week 12 will also be analyzed by fitting the equivalent analysis of covariance (ANCOVA) model, using SAS procedure MIXED to fit an equal-slopes model with terms for prior biologics failure status, baseline CDAI score, and treatment.

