3.3.6. Supplementary Analyses

3.3.6.1. Supplementary Estimand 1

This estimand will follow a composite strategy and has the same components as the Primary Estimand except for the handling of the intercurrent events. Here subjects who have any intercurrent event under treatment failure (ICE 1-5) will have their change from baseline set equal to zero following the ICE. Subjects experiencing intercurrent events (6, 7 and 8) will have their data following the intercurrent event set to missing.

Analysis will follow the same methodology to the primary estimand with missing data after the adjustment for intercurrent events assumed to be MAR.

3.3.6.2. Supplementary Estimand 2

This estimand has the same variable, intercurrent events and population level summary as the primary estimand; however, this estimand has a different population and is defined as below.

Population:

Subjects who reach the Week 12 visit without any major protocol deviations and who enter the study with moderately-to-severely active CD [as defined by a CDAI score of 220-450 and SES-CD score of ≥ 6 (≥ 4 if isolated ileal disease) with ulceration (corresponding to a score of 1) in at least 1 of the 5 ileocolonic segments on the Presence of Ulcers subscore of the SES-CD] who are corticosteroid-dependent or have demonstrated inadequate response or intolerance to conventional therapy (aminosalicylates, corticosteroids and immunomodulators such as azathioprine, 6-mercaptopurine, or methotrexate) or biologics (e.g., anti-TNF therapy, anti-IL-12/23, anti-integrin). A subset of subjects (up to approximately 10%) will have an SES-CD score between 3 and 5 points, inclusive.

Analysis:

An ANCOVA model incorporating the change from baseline in CDAI score at Week 12 as the dependent variable in the model will be used to assess this supplementary estimand.

The model will include independent fixed-effect class terms for treatment group, prior biologic failure status (yes, no) and baseline CDAI score as a covariate.

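### The sensitivity analysis meant to test MAR assumes MCAR instead, and nothing planned relaxes MAR for the primary treatment-policy estimand

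*SAP*

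**What the plan says.** The primary analysis (SAP 3.3.4.1 and 3.3.4.2) is a mixed model for repeated measures (MMRM) on CDAI change at Weeks 4, 8 and 12 in the mITT set, under a treatment-policy estimand. Under SAP 3.3.4.3, missing data, COVID-19 losses included, "will be assumed missing at random (MAR) and accounted for through correlation of repeated measures".

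SAP 3.3.5 lists two sensitivity analyses:
- 3.3.5.1 reads "To assess the impact of the MAR assumption on missing data a sensitivity analysis be performed assuming data is missing completely at random (MCAR". The method is an equal-slopes Week 12 ANCOVA, without imputation, on prior biologics failure, baseline CDAI and treatment.
- 3.3.5.2 repeats the primary analysis with stool frequency removed from the score.

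Protocol 8.5.2 says of MAR: "This assumption will be assessed with a missing data sensitivity analysis if at least one TD-1473 dose is shown to reduce Week 12 CDAI", the comparison being with placebo. Its next paragraph adds: "As a sensitivity analysis, CDAI score change at Week 12 will also be analyzed by fitting the equivalent analysis of covariance (ANCOVA) model", with the same three terms as SAP 3.3.5.1. Protocol 8.9 leaves the method open: "Sensitivity analyses for the primary endpoint will be specified in the SAP".

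Under Supplementary Estimand 1 (SAP 3.3.6.1), subjects with a treatment-failure intercurrent event (ICE 1 to 5) "will have their change from baseline set equal to zero following the ICE". Data after ICE 6 to 8 are set to missing, with "missing data after the adjustment for intercurrent events assumed to be MAR". SAP 3.3.4.2 places it beside the primary result: "The forest plot will also display the differences from placebo for Supplementary Estimand 1".

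**The concern.** A sensitivity analysis of MAR has to let the missing outcomes differ from what the observed data predict. Moving to MCAR goes the other way: MCAR is a special case of MAR, and the ANCOVA also discards the Week 4 and Week 8 data that make MAR more plausible. If the two analyses agree, that is no evidence against not-at-random missingness, because both can be biased in the same direction. If they differ, that suggests MCAR fails but says nothing about whether MAR holds.

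The SAP has in effect taken the ANCOVA already in Protocol 8.5.2 and given it the job of the MAR assessment promised just before it. If a dose is positive, that promise would be met by an analysis that cannot show how far the conclusion depends on MAR.

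**Working it through.** **1. Does any planned analysis relax MAR for the primary estimand?**

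| Analysis | What it changes | Relaxes MAR for the primary estimand? |
|---|---|---|
| Sensitivity 1 (SAP 3.3.5.1) | MAR to MCAR | No, it tightens it |
| Sensitivity 2 (3.3.5.2) | The score | No |
| Supplementary Estimand 1 (3.3.6.1) | Composite strategy, zero change after ICE 1 to 5 | No: different estimand, MAR for the rest |
| Supplementary Estimand 2 (3.3.6.2) | ANCOVA in subjects who reach Week 12 without major deviations | No |
| Nonparametric fallback (3.3.4.2) | Distributional assumptions | No |
| Completeness summaries (3.3.6.6) | Counts missing subscores and ICEs | No: shows how much rests on MAR, does not test it |

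Section 3.3.5 is not redacted, and the SAP contents list shows only these two sensitivity analyses.

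**2. How the two analyses behave under not-at-random missingness.** An illustrative simulation used 60 active and 40 placebo subjects, a true effect of 60, SD 100, an assumed between-visit correlation of 0.6, and active subjects more likely to be missing at Week 12 when their outcome is worse. Regression on Weeks 4 and 8 stood in for the MMRM, and an unadjusted completer comparison for the ANCOVA.

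| Missing | MAR-type estimate | Completer estimate |
|---|---|---|
| about 15% | 66.1 | 71.3 |
| about 20% | 69.0 | 76.2 |

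Both overstate the effect, and the supposed check overstates it more, so the primary result would look conservative beside it.

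**3. Planning figures.** Protocol 8.2 gives 60/60/40 subjects, effects of 45 and 60, residual SD 100, two-sided Hochberg at 5%, and power of 82% (at least one dose) and 58% (both). A z-test simulation with a shared placebo arm gave 80.9% and 56.2%, within 2 points. The steps below use these inputs but not the power.

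**4. Significance limits with complete data.**
- SE = 100 × √(1/60 + 1/40) = 20.41
- Both doses at p ≤ 0.05: 1.960 × 20.41 = 40.01 points
- One dose at p ≤ 0.025: 2.241 × 20.41 = 45.75 points

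**5. Tipping points.** Assume a fraction m is missing and that missing subjects in both active arms are a common δ worse than MAR predicts. The adjusted effect is (effect − m × δ), with Hochberg reapplied. The documents give no missing rate, so m = 0.10 and 0.20 are assumptions; Protocol 6.5.2 mentions more than 10% only as a trigger for replacing subjects.

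Observed effects of 45 and 60:
- 45-point dose: (45 − 40.01)/m = 50 (10%) or 25 (20%).
- 60-point dose, then alone and tested at 0.025: (60 − 45.75)/m = 142 or 71.

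If both doses showed 60: (60 − 40.01)/m = 200 or 100.

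With the SE from observed subjects only:
- 10% missing (54 v 36): SE 21.52, limits 42.17 and 48.23, tipping δ 28 and 118.
- 20% missing (48 v 32): SE 22.82, limits 44.73 and 51.15, tipping δ 1 and 44.

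**6. Benchmark.** If missing active subjects had only the placebo mean, the effect becomes effect × (1 − m):
- 45 becomes 40.5 (10%, borderline against 40.01) or 36.0 (20%, lost).
- 60 becomes 54.0 or 48.0. Both are kept with SE 20.41. With the observed-only SE, 54.0 is kept against 48.23 and 48.0 is lost against 51.15.

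**7. Which Week 12 values are missing?** SAP 3.1.5.1 cuts induction data at last dose + 5 days. SAP 3.3.4.1 uses data after an ICE as collected, and SAP 3.1.3 runs the Week 12 window from Day 77 to Day 98 (or the ATE Day 1 dose, if earlier). A subject who stops between about Day 49 and Day 70 has a nominal End of Study visit 28 days later, on Day 77 to 98. One rule uses that CDAI; the other drops it and leaves it to MAR.

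**The case against.** - **No method was promised.** Protocol 8.5.2 names no technique and 8.9 defers to the SAP, so there is no literal breach. The word introducing the ANCOVA can be read as additional to the mixed model rather than to the MAR check. Protocol 8.9 also makes primary-endpoint sensitivity analyses in general conditional on a positive dose. This stands as far as it goes: the fault is a poor choice of method. But 8.5.2 states the condition for the MAR check and none for the ANCOVA, and on any reading something has to assess MAR.
- **Supplementary Estimand 1 covers the most worrying dropouts.** ICE 5 is discontinuation for worsening disease or lack of benefit, and if placebo subjects improve, zero change is harsher than the placebo-mean benchmark. This is real mitigation, but it answers a composite question and returns to MAR for everything else.
- **The binary CDAI endpoints use non-responder imputation** (SAP 3.4.4.3, COVID-19 losses excepted) and count ICE 1 to 5 as failure (3.4.4.1). They help a reader judge a positive result, but they are different endpoints.
- **The sizes rest on assumptions.** Missing rates are assumed and δ is applied to the active arms only. The tipping value of 1 arises because 45 barely clears 44.73 before any adjustment. All true, and a reason to report the tipping point from actual data.
- **The data-cutoff conflict affects few subjects.** Also true: early stoppers have no scheduled visit in the Week 12 window under either rule, and late stoppers' discontinuation visit can satisfy both. It remains unresolved for those in between.
- **Other untested assumptions remain.** SAP 3.3.2 carries forward up to 4 of the 8 CDAI subscores at a visit. The fix below does not address that.

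**Conclusion.** The concern holds. Sensitivity Analysis 1 cannot do the job it is given, and no other planned analysis shows how far the primary treatment-policy result depends on MAR. Type I error and planned power are unaffected; the weakness lies in interpreting a positive result.

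At planned size, the 60-point target is fairly robust and the 45-point effect is not, partly because 45 sits close to the limit with nothing missing. These sizes rest on SD 100, the assumed missing rates, and planning effects taken as observed. Actual numbers may differ, since SAP 2 restricts mITT by randomization date and excludes two sites. In a Phase 2 trial this should be corrected, but it does not invalidate the primary analysis.

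**What to change.** In SAP 3.3.5.1, relabel the ANCOVA as a complete-case supplementary analysis. If at least one dose is positive, as Protocol 8.5.2 already provides, add:

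- Multiple imputation under MAR using Weeks 4, 8 and 12 and the terms of the primary model.
- A tipping-point analysis that worsens imputed Week 12 CDAI in both TD-1473 arms by a common δ in fixed steps, for example 10 points. Reapply the Hochberg rule of SAP 3.3.3 at each step and report the δ at which each dose loses significance. In the 45/60 illustration with SE 20.41, that grid would give 50 and 150 at 10% missing, and 30 and 80 at 20%.
- COVID-19 missingness held at δ = 0, with a second run that includes it.
- A statement that subjects with no postbaseline CDAI are outside mITT and are not covered.

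Reference-based imputation would also answer the criticism; the tipping point has the advantage of showing the margin directly.

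Separately, reconcile SAP 3.1.5.1 with 3.3.4.1 and 3.1.3, so that it is clear which Week 12 values count as missing.

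The sensitivity analysis costs one paragraph of SAP text and modest programming, run only after a positive result, with no new data. The reconciliation is also a wording change, but it can alter the primary dataset for the few subjects affected, so it should be settled before unblinding.
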